	Subgroup	Post Inj. 3 + 1 year	Post Inj. 3 + 2 years
Group 1	1a	CYD booster	--
	1b	--	CYD booster
Group 2	2a	CYD booster	--
	2b	--	CYD booster
Group 3	3a	CYD booster	--
	3b	--	CYD booster

Each STAGE II subject will provide blood samples for assessing neutralizing Ab titers against each of the 4 parental dengue virus strains. The first blood sample will be collected in all subjects approximately 1 year post last primary series injection (used to assess Ab persistence but also to assess pre-booster Ab levels in subgroup **a**). Subjects receiving the booster injection will provide additional blood samples. Subjects from subgroup **a** will provide a blood sample 28 days after receiving the booster injection. Subjects from subgroup **b** will provide blood samples immediately before and 28 days after receiving the booster injection.

After a dengue seronegative subject consented to continue in the study, the blood sample collected 1 year after the last primary series injection will be the last clinical procedure required from her/him. After this blood sample, a dengue seronegative subject will no longer be asked to come to the study site. However, the telephone contacts already planned in the study will be maintained as a safety follow-up.

Additional Immunological Tests (AIT) Subset –STAGE I and STAGE II

In addition to the blood samples described above, samples will also be drawn from 60 subjects at a specific site in Colombia who consented to participate in additional immunological testing, the additional immunological tests (AIT) subset.

For evaluations of cell-mediated immunity (CMI), Ab specificity and affinity maturation, blood samples will be taken from STAGE I subjects immediately before Injection 1 (specificity, affinity maturation and CMI) and at 28 days following injection 3 (specificity and affinity maturation only).

During STAGE II, only subjects identified as seropositive at baseline and thus eligible to booster injection will continue to be part of the AIT subset. For these subjects, samples will be drawn immediately before the booster injection, and at 7 days, 14 days, and 28 days post-booster injection for CMI, additional neutralizing Abs, Abs specificity and affinity maturation (depending on the time points).

Table S3 presents the subset of study subjects to be tested for CMI, Abs specificity and affinity maturation, following the administration of Year 1 or Year 2 boosters.

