Procedure	Product or Test	V01 (D0)	V02 (V01+ 28d)	V03 (V01+ 6M)	V04 (V03+ 28d)	V05 (V01+ 12M)	V06 (V05+ 28d)	Y1 V07 (V05+ 12M)																				
Injection	CYD or PLA	Inj. 1	Contact visit	Inj. 2		Inj. 3																						
Collection of blood sample:	Neutralizing Abs (all subjects)	BL1* (pre-inj. 1) 5 mL	N/A	BL2* (pre-inj. 2) 5 ml	BL3 5 mL	BL4* (pre-inj. 3) 5 mL	BL5 5 mL	BL6† 5 mL																				

Table S9: STAGE II injection and blood sampling schedules (all subjects)

Procedure	Group	Y1 V07 (V05 + 12M)	Y2 V07 (V05 + 24M)	V10 (V07+28d)	6M Follow-up
Injection	1a, 2a, 3a	Booster Y1			PC
	1b, 2b, 3b		Booster Y2		PC
Collection of blood sample:	1a, 2a, 3a	BL6 (pre-Booster)*†		BL9†	PC
	1b, 2b, 3b	BL6;	BL10 (pre-Booster)†‡	BL13†‡	PC

* In the context of STAGE I, BL6 will be used to assess neutralizing Abs persistence at 1 year post last primary series injection. In STAGE II, BL6 will be used assess to neutralizing Ab levels at pre-booster injection for subjects from subgroup a that were seropositive at baseline

† This includes the volume to assess Ab specificity and affinity maturation.

‡ Only subjects identified as seropositive at baseline will provide BL10 and BL13

AIT Subset

In STAGE I, a subset of 60 subjects in groups 1a, 1b, 2a, 2b, 3a, 3b (10 each group) will provide additional blood before Injection 1 and 28 days after the injection, and again, in STAGE II, immediately before the Y1 or Y2 CYD booster injection and 7, 14, and 28 days after the booster dose for measurement of CMI response (Table S8).

Table S10: STAGE II Additional blood samples (AIT subset)

Procedure	Group	Product or Test	Y1 V07 (V05 + 12M)	Y2 V07 (V05 + 24M)	V08 (V07 + 7d)	V09 (V07 + 14d)	V10 (V07 + 28d)
Injection	1a,2a,3a	CYD Booster dose	Booster Y1				
	1b,2b,3b	CYD Booster dose		Booster Y2			
Blood Sampling*	1a,2a,3a 1b,2b,3b	CMI response	BL6	BL10	BL7 or BL11	BL8 or BL12	BL9 or BL13
		Additional neutralizing Abs; Abs specificity			BL7 or BL11	BL8 or BL12	

* BL6 will be taken in all subjects; BL10 will be taken in subgroup b only; BL7-BL9 will be taken in subgroups 1a, 2a, and 3a only; BL11-13 will be taken in subgroups 1b, 2b, and 3b only

Only the subjects identified as seropositive at baseline will provide BL7–BL10 or BL10-BL13, depending on the subgroup

STAGE I and II:

Additional biological samples may be collected from any subject in case of the occurrence of SAEs (including VCD cases) during the trial.

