30-min observation period	√		√		√				subgroup a: V07 Y1 subgroup b: V07 Y2		√	√	√	
Injection site reactions & systemic events§§	√	√	√	√	√	√								
Diary Card (DC): Provided:	DC1		DC2		DC3				DC4 or DC4 Group b or MA2	DC5				
Checked and/or collected:		DC1		DC2		DC3			***	DC4 Group b ***	DC4/DC5	DC4/DC5	DC4/DC5	
Memory Aid (MA): Provided:						MA1								
Checked:							MA1		MA1				MA2	MA2
Termination Record													√	
SAEs and Serious AESIs†††	To be reported throughout the study period													
THE FOLLOWING ADDITIONAL PROCEDURES APPLY ONLY TO THE AIT SUBSET														
Additional neutralizing Ab											BL7 or BL11‡‡	BL8 or BL12‡‡		
Affinity maturation and specificity assays	BL1					BL5			BL6‡‡	BL10‡‡	BL7 or BL11‡‡ ‡‡‡	BL8 or BL12‡‡ ‡‡‡	BL9 or BL13‡‡	

STAGE I							STAGE II*							
Visit Number (V)	V01	V02	V03	V04	V05	V06	6M FU (PC7)†	V06-Inf	V07 (Y1)	V07 (Y2)	V08 (Y1/Y2) (AIT only)	V09 (Y1/Y2) (AIT only)	V10 (Y1/Y2)	6M FU (PC)‡
Trial timelines (Days/Months)	V01	V01+ 28d	V01+ 180d	V03+ 28d	V01+ 365d	V05+ 28d	last inj + 6M		V05+ 12M	V05+ 24M	V07+ 7d	V07+ 14d	V07+ 28d	V07+ 6M
Time Windows (Days)		+14d	±20d	+14d	±20d	+14d	+20d		+60	+60	+3d	+7d	+14d; +7d AIT only)	+20d
CMI	BL1								BL6‡‡	BL10‡‡	BL7 or BL11‡‡	BL8 or BL12‡‡	BL9 or BL13‡‡	

NAb: neutralizing antibodies; CMI: cellular mediated immune response; Aff: affinity; AIT: Additional Immunological Testing subset.

- * As describe in the synopsis, dengue seronegative subjects at baseline will attend Y1 V07 and have the possibility to provide BL6 once having consented to continue in the trial. After the Y1 V07, they will no longer have to come back to the site.
- † See Table of procedures (Phone Contacts). Subjects having prematurely terminated the trial will be contacted by phone for the 6-month safety follow-up.
- ‡ See Table of procedures (Phone Contacts). Subjects eligible to booster injection will be contacted by phone for the post-booster injection 6-month safety follow-up (PC12 for subjects from subgroup a and PC15 for subjects from subgroup b). Subjects non-eligible to booster injection will be contacted by phone as part of the safety follow-up.
- § Axillary temperature will be obtained for vaccination visits; also, note that febrile illness on the day of vaccination is a temporary contraindication.

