- ** Urine pregnancy test for females of child-bearing potential; to be considered of non-child-bearing potential, a female must be post-menopausal for at least 1 year, surgically sterile, or using an effective method of contraception or abstinence from at least 4 weeks prior to vaccination and until at least 3 weeks after vaccination
- †† Blood samples planned during vaccination visits will be taken before injection. Baseline YF and JE status will be assessed using PRNT.
- ‡‡ BL6 is to be taken in all subjects 1 year after last injection (at V05 + 12M). BL10 is to be taken in subjects from subgroup b 2 years after last injection (at V05 + 24M). BL7 through BL9 are taken in subgroup a only; and BL11 through BL13 are taken in subgroup b only.
- §§ Solicited injection site reactions will be collected for 7 days after injection. Solicited systemic reactions will be collected for 14 days after injection. Unsolicited AEs will be collected for 28 days after injection.
- *** DC4 will be provided to subgroup a to collect the full safety information after booster injection at Y1. DC4 Group b will be provided to subgroup b to collect SAEs from V07 Y1 to V07 Y2. DC5 will be provided to subgroup b to collect full safety information after booster injection at Y2. Dengue seronegative subjects at baseline from both subgroups will be provided with MA2.
- ††† Serious AESIs will be reported after each injection in defined time windows as follows: serious hypersensitivity/allergic reactions occurring within 7 days, serious viscerotropic disease occurring within 30 days, serious neurotropic disease occurring within 30 days; hospitalized suspected dengue disease will be reported during the entire study. Non-serious AESIs (ie, hypersensitivity / allergic reactions) will be reported within 7 days after each injection.
- ‡‡‡ At these time points, Ab specificity may be assessed, if necessary; Ab affinity maturation will not be assessed.

Table of Procedures – Phone Contacts

	STAGE I									STAGE II					
Phone Contact (PC)	PC1	PC2	PC3	PC4	PC5	PC6	PC7*	PC8	PC9	PC10	PC11	PC12*	PC13†	PC14†	PC15†
Trial timelines (Days/Months)	V01+ 2M	V01+ 4M	V01+ 8M	V01+ 10M	V01+ 14M	V01+ 16M	V01+ 18M	V01+ 20M	V01+ 22M	V05 + 14M	V05 + 16M	V05 + 18M	V05 + 20M	V05 + 22M	V05 + 30M
Time Windows (Days)	+8d	+8d	+8d	+8d	+8d	+8d	+20d	+8d	+8d	+8d	+8d	+8d	+8d	+8d	+20d
Ask about SAEs not yet reported‡	√	√	√	√	√	√	√	√	√	√	√	√	√	√	√

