5.1.3.2 AIT Subset

The analyses for AIT subset are based on the following:

Dengue PRNT (at V01, V06, V07, V08, V09 and V10): neutralizing Ab levels against each of the four parental dengue virus strains as determined by PRNT.

CMI responses (at V01, V07, V08, V09 and V10):

- Cytokine secreting CD4 and CD8 T cells count (at V01, V07, V08, V09 and V10)

Note: The raw individual results will not be directly described in the analysis: the results of all stimulations will be corrected with the corresponding medium result. The detailed calculation is below:

For envelope (ENV) CYD 1, ENV CYD 2, ENV CYD 3, ENV CYD 4, NS3 peptide pools from YF 17D and DEN, and positive control, the medium (MED) = value of the negative control medium.

Therefore, the following corrected endpoints will be used:

- Before vaccination: $X_{D0} - MED_{D0}$ where X is the value of ENV CYD 1, ENV CYD 2, ENV CYD 3, ENV CYD 4, positive control or NS3 peptide pools from YF 17D and DEN, etc.
- 28 days after vaccination: $X_{D28} - MED_{D28}$,
- 12 months after vaccination: $X_{M12} - MED_{M12}$,
- Change from baseline endpoints (ratio): $(X_{D28} - MED_{D28}) / (X_{D0} - MED_{D0})$ and $(X_{M12} - MED_{M12}) / (X_{D0} - MED_{D0})$.
- Change from D28 endpoints (ratio): $(X_{M12} - MED_{M12}) / (X_{D28} - MED_{D28})$.
- T cell subpopulation (naïve, effector, central and terminally differentiated memory T cells) count (at V01, V07, V08, V09 and V10)

Note: Naïve T cells are defined as CD45RA+ and CCR7+, effector memory T cells defined as CD45RA- and CCR7-, central memory T cells defined as CD45RA- and CCR7+, and terminally differentiated memory T cells as CD45RA+ and CCR7-.

- No corrected value will be used for the subpopulation analyses. Only the raw value of the medium, ENV CYD1, ENV CYD 2, ENV CYD 3, ENV CYD 4, positive control or NS3 peptide pools from YF 17D and DEN will be summarized.
- Cytotoxic T cell effector markers (at V01, V07, V08, V09 and V10)

Note: The functional markers are including IFN γ , TNF α , IL-2, MIP-1 β and CD107a for CD3+ CD8+ T cells, and have one more marker CD154 for CD3+ CD4+ T cells. The

cytotoxic T cell will be also summarized for activated cells, simple positive cells, double positive cells, triple positive cells and more than triple positive cells. The definition for different cells are:

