- Activated cells: Positive for at least one of the following markers IFN γ /TNF α /IL-2/MIP-1 β /CD107a for CD3+ CD8+ cells and IFN γ /TNF α /IL-2/MIP-1 β /CD107a/CD154 for CD3+ CD4+ cells
- Simple positive cells: Activated cells which express 1 of the following markers IFN γ /TNF α /IL-2/MIP-1 β /CD107a for CD3+ CD8+ cells and IFN γ /TNF α /IL-2/MIP-1 β /CD107a/CD154 for CD3+ CD4+ cells
- Double positive cells: Activated cells which express 2 of the following markers IFN γ /TNF α /IL-2/MIP-1 β /CD107a for CD3+ CD8+ cells and IFN γ /TNF α /IL-2/MIP-1 β /CD107a/CD154 for CD3+ CD4+ cells
- Triple positive cells: Activated cells which express 3 of the following markers IFN γ /TNF α /IL-2/MIP-1 β /CD107a for CD3+ CD8+ cells and IFN γ /TNF α /IL-2/MIP-1 β /CD107a/CD154 for CD3+ CD4+ cells
- More than triple positive cells: Activated cells which express 3 of the following markers IFN γ /TNF α /IL-2/MIP-1 β /CD107a for CD3+ CD8+ cells and IFN γ /TNF α /IL-2/MIP-1 β /CD107a/CD154 for CD3+ CD4+ cells

In addition, the number of responders to the ICS test by stimulation will be computed. To be considered as responders the two following conditions must be filled:

$$\frac{X_{post-booster} - MED_{post-booster}}{X_{D0} - MED_{D0}} \geq 2$$

$$[X_{post-booster} - MED_{post-booster}] - [X_{D0} - MED_{D0}] \geq 0.05\%$$

- The post-booster visits here are D28 and M12
- Ex vivo B cells (plasmablast) count (measured by ELISPOT) (at V01, V07, V08 and V09)
- Number of antibody secreting cells (ASC) for each of the four specific parental dengue virus strains IgG and the total IgG will be summarized.
- Memory B cells count (measured by ELISPOT) (at V01, V07, and V10)

Note: Antibody secreting cells (ASC) for each of the four specific parental dengue virus strains IgG and the total IgG will be summarized. In addition, for each of the four specific parental dengue virus strains IgG, the ratio will be also calculated. The ratio (%) can be obtained by:

$$\text{Ratio} = \frac{\text{ASC for CYD1/2/3/4 IgG}}{\text{ASC for Total IgG}} \times 100\%$$

Ab specificity and affinity maturation:

- The neutralizing Abs in the wide-type dengue parental strains (DENV) depleted, BSA-control depleted sera and whether the response is homotypic for each of the four parental dengue virus strains will be assessed (at V01, V06, V07, V08, V09 and V10).

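### SAP 5.1.3.2 (exploratory AIT subset): the ICS responder rule names a post-booster month-12 visit with no scheduled sample, one marker class repeats another, and corrected baselines at or below zero are unhandled

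*SAP*

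**What the plan says.** **Visits and responder rule.** SAP 5.1.3.2 gives the sampling for cell-mediated immunity (CMI) as "CMI responses (at V01, V07, V08, V09 and V10". It then defines medium-corrected values, X − MED, under three labels: D0 (before vaccination), D28 and M12 (28 days and 12 months after vaccination). Ratios to D0 are planned, and under "Change from D28 endpoints (ratio" also M12 over D28. A subject is an intracellular cytokine staining (ICS) responder if the corrected post-booster value is at least twice the corrected D0 value and the difference is at least 0.05%. A note adds: "The post-booster visits here are D28 and M12".

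**Marker classes.** Triple positive is defined by three markers. The next class reads "More than triple positive cells: Activated cells which express 3 of the following markers".

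**Schedule.** Protocol 7.1.2 names the same five CMI visits. The footnotes to SAP Table 3.1 (in 3.2) say "Blood samples planned during vaccination visits will be taken before injection", and that booster-eligible subjects are later "contacted by phone for the post-booster injection 6-month safety follow-up".

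**Sampling after Injection 3.** The protocol is not uniform. The Synopsis paragraph on the AIT subset has blood drawn "at 28 days following injection 3 (specificity and affinity maturation only". The Synopsis schedule of procedures says the subset "will provide additional blood before Injection 1 and 28 days after the injection", in a sentence that ends with CMI measurement.

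**Value handling.** SAP 4.4.1.1 covers titers below LLOQ or above ULOQ. SAP 5.3.1 refers back to it and adds that missing data are not imputed. SAP Table 5.1 and the end of 5.1.3.2 plan log10 means, SDs and geometric means for continuous CMI data.

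**The concern.** Three stated rules give a wrong or undefined result when followed.

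- The responder rule calls M12 a post-booster visit, but the schedule has no CMI sample that fits.
- Two marker classes share one definition, so two table rows would count the same thing.
- Subtracting the medium result can leave a baseline at or below zero. The fold-rise condition then fails or is undefined, whatever the response.

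If nothing changes, the programmer has to settle these choices outside the plan. Two subjects with the same post-booster value could be scored oppositely because background subtraction left one baseline just below zero. With at most 10 subjects per subgroup, one misclassified subject moves a responder rate by 10 percentage points or more.

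**Working it through.** The plan gives no figure to reproduce, so the check sets the schedule against the labels and works through the rule.

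**1. Schedule, in months from Injection 3 (V05 = 0).** Visit timings are from the Table of Procedures and the phone-contact table; V10 is booster + 28/30.44 months.

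| | Subgroup a | Subgroup b |
|---|---|---|
| Booster (V07) | 12 | 24 |
| V10 | 12.9 | 24.9 |
| 6-month phone call | 18 | 30 |
| 12 months post-booster | 24 | 36 |

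For subgroup a, month 24 is when BL10 is drawn, but only in subgroup b. For subgroup b, month 36 falls after the last contact at month 30. So neither subgroup has a post-booster M12 sample.

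Other readings of M12:

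- V05 + 12 months is BL6. In subgroup a it is drawn before the booster injection; in subgroup b it comes a year before the booster.
- V01 + 12 months is V05, where no CMI blood is drawn.

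D28 as V06 would make M12/D28 a persistence ratio. One Synopsis sentence suggests CMI blood at that visit. Against it stand the Synopsis AIT paragraph, Table S3 (no CMI volume after Injection 3), the Table of Procedures, Protocol 7.1.2, SAP 3.2 and the SAP 5.1.3.2 visit list. If V10 is the only D28 CMI sample and M12 is BL6, the ratio puts an earlier sample over a later one.

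**2. Marker classes.** CD8 cells have 5 functional markers and CD4 cells have 6. If three means exactly three, cells with four or more markers fall only under activated cells. That is 5 + 1 = 6 of 2^5 − 1 = 31 CD8 marker combinations, and 15 + 6 + 1 = 22 of 2^6 − 1 = 63 CD4 combinations. These are combinations, not cell frequencies. If three means at least three, the two classes still coincide.

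**3. Responder rule.** Let b be the corrected baseline and p the corrected post-booster value. The rule needs p/b ≥ 2 and p − b ≥ 0.05%.

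- b > 0: both hold when p ≥ max(2b, b + 0.05%). For b ≤ 0.05% the difference condition decides alone, because 2b ≤ b + 0.05%. The cut-off is 0.051% at b = 0.001%, 0.06% at 0.01% and 0.10% at 0.05%. Above that the ratio decides (0.12% at 0.06%).
- b = 0: the ratio is undefined.
- b < 0: p/b ≥ 2 gives p ≤ 2b < b, while the difference condition gives p ≥ b + 0.05% > b. These contradict each other, so no value of p makes a responder.

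Example with p = 0.20%:

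| b | Ratio | Difference | Result |
|---|---|---|---|
| +0.001% | 200 | 0.199% | responder |
| 0 | undefined | 0.20% | not assignable |
| −0.001% | −200 | 0.201% | non-responder |

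Logs and geometric means are likewise undefined for any corrected value at or below zero.

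**The case against.** The strongest reply is that these are drafting gaps in a descriptive, exploratory analysis that itself allows for further analyses, and that a competent programmer would see the intent. The marker error in particular is obvious from its label. That bears on severity, and it stands. It does not settle the visit labels or the negative-baseline case, where the intended handling cannot be read from the text. The list of changes in SAP 5.7 does not address them either.

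A reader might go further than the documents allow in several ways.

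- *No 12-month CMI sample exists.* Not so: BL6 is scheduled 12 months after Injection 3. What is missing is a post-booster month-12 sample.
- *The responder table will be wrong.* The labels are not mapped to visits, and SAP 5.1.3.2 limits the analyses to available time points, so an empty M12 column is equally possible.
- *D0 must be V01.* Protocol Tables S3 and 5.4 use D0 for both the pre-Injection 1 and the pre-booster sample, and Protocol 9.3.1.2.2 pairs D0 with D28 post-booster. The documents do not say which one the rule uses.
- *All corrected values should be floored.* That would change results for positive baselines that now work. With b = 0.01% and p = 0.08%, the rule gives ratio 8 and difference 0.07%, a responder. A floor of 0.05% gives ratio 1.6 and difference 0.03%, a non-responder.

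**Conclusion.** The point holds as a minor one. As specified, the responder rule names a post-booster time point without a scheduled sample, one marker class duplicates another, and a subject with a negative corrected baseline can never be a responder.

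The reach is at most 60 subjects: 10 per subgroup, 20 per group, 30 per booster year, and fewer once Stage II is restricted to baseline-seropositive subjects. No primary or secondary conclusion depends on it.

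The schedule finding assumes that no CMI samples were taken outside the listed visits. The algebra needs no assumption beyond the two stated conditions. The practical effect of the third gap is unknown: the documents give no ICS mean, SD or background level, so it would be unsupported to infer that non-positive baselines are common, or that they are rare.

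**What to change.** In SAP 5.1.3.2:

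- Map D0, D28 and M12 to named visits, and state whether D0 in the responder rule is V01 or the pre-booster V07 sample.
- Replace D28 and M12 in the responder rule with the post-booster visits sampled: V10, and also V08 and V09. The last two are protocol T-cell time points (Protocol 9.3.1.1) that the corrected endpoints and the rule now omit.
- Keep V07 Year 1 only as a persistence or pre-booster time point. Drop the M12/D28 ratio unless V06 CMI samples exist.
- Reconcile the Synopsis schedule sentence on blood 28 days after the injection with the Synopsis AIT paragraph, Table S3, the Table of Procedures, Protocol 7.1.2 and SAP 3.2.
- Define the class above triple positive as four or more markers (4–5 for CD8, 4–6 for CD4).
- For b ≤ 0, let the 0.05% difference condition alone decide responder status, and leave the rule for positive baselines unchanged. This joins smoothly, since that condition already decides alone for 0 < b ≤ 0.05%. For b below −0.05% the cut-off b + 0.05% is itself negative, so the laboratory should confirm that this is acceptable.
- For logs, ratios and geometric means, prespecify an assay-justified handling of corrected values at or below zero. The documents give no ICS detection limit, so no value is proposed here.

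The cost is SAP wording and programming. No new samples are needed.

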5.1.4 Complementary output

Additional analyses by baseline dengue and YF/JE statuses will be provided in Appendix 15 of the CSR.

Safety analyses:

- Overview and summary tables of AEs
- SAEs including serious AESIs by SOC and PT
- Non-serious AESIs by SOC and PT

5.2 Analysis Sets

Six analysis sets will be used: PPAS, FAS, SafAS, the enrolled subjects set, the randomized subjects set, and the AIT subset.

5.2.1 Per-Protocol Analysis Set

The per-protocol analysis set (PPAS) will include all subjects who had no protocol violations as defined below and will be defined for both stages as follows:

STAGE I:

The subjects who will be vaccinated but who meet any of the following study violations will be excluded from the PP set in STAGE I:

- Subject did not meet all protocol-specified inclusion/exclusion criteria or definitive contraindications
- Subject did not receive the correct number of doses or injections
- Subject received a vaccine other than the one that he/she was randomized to receive
- Administration of vaccine at V05 was not done as per protocol (site and route of administration)
- Subject did not receive vaccine at V05 in the proper time window (V01 +365 days \pm 20 days) defined in the tables of the study procedures
- Subject did not provide a V06 post-dose serology sample in the proper time window (V05 +28 days \pm 14 days)
- Subject received a protocol-restricted medication, therapy, or vaccine in STAGE I as defined in Section 6.7 of the protocol.
- Subject's post-injection serology samples at V06 did not produce a valid test result (i.e. a result different from "not-reportable" ['NR'] or missing, for at least one dengue serotype).

STAGE II:

The subjects who will be vaccinated but who meet any of the following study violations will be excluded from the PPAS in STAGE II:

- Subject did not meet all protocol-specified inclusion/exclusion criteria or definitive contraindications
- Subject did not receive the correct number of doses or injections
- Subject had negative dengue serostatus at baseline.
- Subject received a vaccine other than the one that he/she was randomized to receive
- Administration of vaccine at V07 was not done as per protocol (site and route of administration)
- Subject did not receive vaccine at V07 in the proper time window defined in the tables of the study procedures
- Subject did not provide a V10 post-dose serology sample in the proper time window
- Subject received a protocol-restricted medication, therapy, or vaccine in STAGE II as defined in Section 6.7 of the protocol.
- Subject's post-injection serology samples at V10 did not produce a valid test result (i.e. a result different from "not-reportable" ['NR'] or missing, for at least one dengue serotype).
- Subjects randomized to Group 1 not included in the PP set in STAGE I

